#### VERSION DATE: 03/11/2021

#### **REVISION HISTORY**

Version #	Version Date	Summary of Changes	Consent Change?
1	9/16/18	Initial submission	No
2	1/23/19	Removed pre-/post-EEG during tDCS sessions 1-10, questionnaire updates, changing total at-home MBT training to 4 weeks, changes in recruitment and assessments	Yes
3	2/4/19	Added new titles corresponding with grants, updating times and adding procedure details, added PSQI, removed emotion regulation task.	Yes
4	3/4/19	Expanded age range, updated payment, added future re-contact.	
5	3/21/19	Added recruitment from clinic, re- administering the MINI depression module post-intervention, clarified study details, changed randomization to be based on sex only	
6	4/26/19	Made MRI optional and clarified procedures in the case of poor data quality and technical errors, updated outcomes to be consistent with aims, clarified details about MBT, added stress biology measurements, updated compensation, and added new recruitment material	Yes
7	8/1/19	Updates to recruitment materials and increased flexibility about rescheduling sessions	No

8	8/14/2019	Changed procedure for MRI	No
		toxicology screen to reflect that	
		participants will be scanned if	

		results are positive, and we have	
		taken out language that stated the	
		PI will be called if results are	
		positive since recent drug use is	
		not a safety issue.	
0	0/11/2010	-	Na
9	9/11/2019	Remote completion option for	No
		REDCap self-report online	
		questionnaires has been added to	
		increase flexibility with	
		questionnaire completion when	
		participants have time constraints	
		at in-person appointments.	
10	10/18/2019	1) Change in phone screen process	No
		involves the addition of an online	
		eligibility survey link (MADRS-S	
		via REDCap). Completion of	
		MADRS-S during the phone screen	
		will help reduce participant and	
		staffing burden by allowing staff to	
		know which participants meet the	
		basic requirement of eligibility	
		(MADRS-S score of 13 or more).	
		2) Added standardized language	
		provided by CMRR, approved by	
		the IRB regarding usage of CMRR	
		subject safety screening forms.	
		3) Change in procedure for	
		completing 3 weeks of mindful	
		breathing training- participants will	
		be given the option of doing it in	
		person only if the study team	
		determines it would be helpful for the participant.	
11	1/16/2020	· · ·	No
11	1/16/2020	1) Added language regarding the	No
		risks of using text messaging and	
		email communication with	
		participants.	
		2) REDCap questionnaire (Cash	
		Choice Task) added.	
		3) Clarified that the post-tDCS EEG	
		and MRI will be completed within	
		1-2 business days, instead of 1-2	
		days.	

1	1		· · · · · · · · · · · · · · · · · · ·
		
 
4) Added clearer language stating that participants are not required to complete all five mindful breathing sessions during the ramp-up period in order to begin in-person tDCS and mindful breathing.
 
5) Added new location (Department of Psychiatry at Park Plaza) for consenting and conducting clinical intervNAiews. Clarified that the Center for Neurobehavioral Development is used for consenting and clinical interviews.
 
	
12	3/18/2020	
 
Changed study exclusion criteria- removed "family history of epilepsy" as this is not a safety concern for tDCS.
 
Changed inclusion criteria regarding study population to Female, 17 to 24 year old, in order to decrease sample heterogeneity.
 
	No
13	3/24/2020	Remote completion option for study procedures due to COVID-19.	No
14	6/8/2020	Took out language stating that participants will be randomized according to sex since the study is now recruiting females only. Added language regarding withdrawal of participants who appear to be unduly stressed (section 12.1).	Yes
15	8/28/2020	Included language to allow flexibility about repeating visits if there is a delay between baseline visits and the start of tDCS and MBT.	Yes
16	11/04/2020	Included language to allow participants to be screened using	Yes

		REDCap surveys. Updated recruitment materials for phone number.	
17	3/11/2021	Clarified in the protocol that the MADRS-S may be repeated if clinically indicated	No

#### ABBREVIATIONS/DEFINITIONS

- AAI: Alpha asymmetry Index
- DLPFC: Dorsolateral prefrontal cortex
- DMN: Default Mode Network
- ECG: Electrocardiographic
- EEG: Encephalography
- ERN: Error-related negativity
- ERP: Event-Related Potential
- HRV: Heartrate variability
- LPP: Late Positive Potential
- MDD: Major Depressive Disorder
- MRI: Magnetic Resonance Imaging
- MBT: Mindful Breathing Training
- RSFC: Resting state functional connectivity
- tDCS: Transcranial Direct Current Stimulation

#### 1.0 Objectives

1.1 Purpose: This study will investigate whether transcranial direct current stimulation (tDCS) targeting the dorsolateral prefrontal cortex (DLPFC) can enhance the therapeutic effect of mindful breathing training (MBT) for adolescent depression. The objective is to enhance connectivity between the DLPFC with the amygdala and Default Mode Network (DMN) circuits as well as to enhance emotion regulation abilities and decrease rumination to reduce symptoms of depression. This will aid in the development of novel treatments for depression.

*1.2* This study will investigate the following aims:

**Aim 1**: To demonstrate the feasibility of recruiting and randomizing adolescents with depression to a research protocol involving MBT and tDCS. We expect that adolescents will be willing to enroll in a randomized trial involving MBT and tDCS.

**Aim 2**: To test the tolerability of MBT and tDCS in adolescents. We expect that MBT will be well-tolerated and that active tDCS will show no difference in tolerance compared to sham stimulation.

**Aim 3**: To examine whether tDCS can enhance the effects of MBT. We expect the MBT + tDCS group will show greater reduction in depressive symptoms compared to the MBT + sham stimulation group.

**Aim 4:** To examine the mechanisms of MBT +/- tDCS treatment. We expect that depression symptom improvement will be associated with decreased rumination, improvements in emotion regulation, increased task-based and resting state DLPFC-DMN and DLPFC-amygdala connectivity, as well as increased DLPFC activation and reduced amygdala activation during rumination and emotion processing tasks. We also expect reduced alpha asymmetry and reduced LPP amplitude during emotion regulation and emotion processing. We expect these changes will be greatest in the active tDCS + MBT group.

#### 2.0 Background

2.1 Significance of Research Question/Purpose:

Depression, the main contributor to disability globally and a significant risk factor to premature deaths due to suicide (Friedrich, 2017), commonly arises in adolescence (Kessler et al., 2005). Forty percent of depressed adolescents do not adequately respond to existing treatments (March et al., 2004), emphasizing the urgent need to identify novel, biologically-based treatments. Recent neuroscience research has begun shed light on the pathophysiology of depression, implicating impairments in frontolimbic circuitry, including 1) an underactive dorsolateral prefrontal cortex (DLPFC), a region that supports executive control and emotion regulation (Disner,

Beevers, Haigh, & Beck, 2011; Koenigs & Grafman, 2009) and 2) an overactive amygdala, a region implicated in the experience of negative affect (Drevets, 2006). Connectivity between DLPFC and amygdala is also reduced in depression (Lu et al., 2012). Abnormal hypothalamic pituitary adrenal (HPA) functioning has been found in depression (Burke, Davis, Otte, & Mohr, 2005; Vreeburg et al., 2009) and with rumination (Zoccola & Dickerson, 2012). Since these brain systems are still undergoing development during adolescence (Luciana, 2013), the adolescent years represent a critical time during which to advance understanding of the neural basis both of depression and of novel treatments.

Transcranial direct current stimulation (tDCS) is a non-invasive neuromodulation technique that can modulate neural activity. If paired with MBT, tDCS may be able to enhance learning and neural changes associated with MBT. This study will test the efficacy of a novel treatment comprised of MBT and tDCS and will be the first to implement tDCS in adolescent depression. We propose that for patients with depression, where the core feature is persistent negative mood, a training task that engages the DLPFC's role in regulating emotion may optimally reduce symptoms of depression. Mindful breathing training (MBT) may be a suitable task to down-regulate negative affect and prime the fronto-limbic circuit. Further, this work will advance our understanding the synergistic effects of combining MBT with tDCS to target the connections between the DLPFC with the default mode network (DMN) and limbic regions. If successful, this study will aid in the development of novel treatments for adolescent depression and improve the ability of neuromodulation to treat depression. This would improve public health by promoting remission, reducing poor outcomes like suicide, and reducing the economic burden of depression.

#### 2.2 Preliminary Data:

Drs. [name], [name], [name] and [name] have conducted foundational research identifying possible targets of intervention. Using resting-state fMRI, we previously showed in 43 unmedicated adolescents with depression versus 35 controls that patients had greater resting-state functional connectivity between amygdala (a brain region that is critically involved in negative emotion) and the precuneus (a key node of the default mode network) ([name] et al., 2014). These findings inspired us to further pursue the interactions between DMN and salience network in adolescents at risk for suicide as proposed here.

Drs. [name] and [name]'s collaborations have documented the feasibility for conducting intervention studies, including those employing

neuromodulation techniques (transcranial magnetic stimulation; TMS), in adolescents with depression ([name] et al., 2016). Notably, this TMS protocol required 30-daily TMS intervention visits in addition to pre- and post- MRI and assessment visits.

2.3 Existing Literature:

Mindfulness-based interventions (MBI), which include MBT, involve focusing on the present experience. During MBI, one becomes aware of mind-wandering, disengages and shifts attention back to the present experience. In depression, this can serve to regulate emotion by redirecting attention away from spontaneous thoughts, which tend to be negative and ruminative in nature. MBI has been shown to improve emotion regulation abilities and to reduce negative affect (Keng, Smoski, & Robins, 2011). Neurally, MBI may be able to prime the connections between the DLPFC with limbic and DMN regions as mindfulness has shown to activate the DLPFC (Hasenkamp & Barsalou, 2012), reduce amygdala activation (Goldin & Gross, 2010), increase connectivity between the DLPFC and the amygdala (Hölzel et al., 2013) and increase connectivity between the DLPFC and the DMN (Jang et al., 2011; King et al., 2016).

Transcranial direct current stimulation (tDCS) is a safe and cost-effective technique that has been studied in adult depression, typically targeting the DLPFC (Kalu, Sexton, Loo, & Ebmeier, 2012). Notably, the DLPFC subserves multiple regulatory functions, including emotional and non-emotional behavior. Prior neuroimaging studies have shown that tDCS stimulating the left DLPFC upregulates DLPFC activity, can decrease amygdala activity (Ironside et al., 2017) and increase connectivity between the DLPFC and the DMN (Keeser et al., 2011). Although tDCS has been shown to be safe for adolescents (Krishnan, Santos, Peterson, & Ehinger, 2015), its efficacy for adolescent depression has yet to be explored (Vicario & Nitsche, 2013). Further, while adult depression studies have demonstrated effectiveness of tDCS versus sham, the effect size has been only small to moderate (Hedge's g = 0.74), with response rates, ranging from 0-80% and only an average of 8.5% of patients achieve full remission with tDCS (Kalu et al., 2012), highlighting significant room for improvement with this treatment.

An important advance in this line of work shows that the effects of MBT and tDCS may interact synergistically. tDCS establishes a neuroplastic state which can accelerate the learning and neural effects of mindful breathing (Fritsch et al., 2010). The effects of tDCS can be augmented by priming the targeted neural networks by having participants perform a task that requires activation of the targeted neural system in conjunction with stimulation (Romei, Thut, & Silvanto, 2016). In adult depression, cognitive

control training has been combined with tDCS to enhance DLPFC activity with a response rate of 25-44% (Brunoni et al., 2014; Segrave, Arnold, Hoy, & Fitzgerald, 2014).

#### **3.0** Study Endpoints/Events/Outcomes

3.1 Primary Endpoint/Event/Outcome: Primary outcome measures of feasibility and tolerability include side-effects, number of participants enrolled, and dropout rate. The primary clinical outcome measure will be change in depression symptoms and DLPFC connectivity with the salience network and the default mode network.

3.2 Secondary Endpoint(s)/Event(s)/Outcome(s): Additional outcomes may include mindfulness, rumination, cortisol, cognition as assessed by executive functioning tasks, change in biological measures (e.g., RSFC, task-based neural activation, alpha asymmetry, and LPP amplitude),

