#### 5.0 Procedures Involved

5.1 Study Design: Participants will undergo ten daily sessions of one of two conditions: 1) active tDCS + Mindful Breathing Training or 2) sham tDCS + Mindful Breathing Training (approximate final n of 15 per group). A randomized block design will be used to assign each subject to a condition (sham or active tDCS). This study will be double-blind to +/- tDCS stimulation.

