#### 6.0 Data and Specimen Banking

Storage and Access: Study data will be managed by Co-Investigator [name]. Data will be deidentified using an arbitrary identification number assigned to each participant. Personally-identifiable information, including participant names, birthdates, and contact information, will be maintained in order to contact patients. This personally identifiable information will be kept separately in an encrypted, password-protected file kept separate from study data. A separate file linking identifiers with identification numbers will be stored separately. Phone screen information will only be kept for participants who participate in the consent visit; this will be stored in locked cabinets. Phone screen information from individuals who do not qualify based on the phone screen or who decide not to enroll will be shredded.

Data: Include clinical assessments, self-report measures, behavioral task performance data, technical aspects of neuromodulation sessions, MRI scan data, EEG data, and ECG data. De-identified neuroimaging data will be stored locally on servers supported by the Center for Magnetic Resonance (CMRR). De-identified clinical, EEG, ECG, and behavioral data will be stored in a secure, HIPAA-compliant REDCap database and Box Secure Storage supported by the university of Minnesota or on local servers.

Release/Sharing: Data will only be released in deidentified form to research collaborators.

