#### **10.0** Local Number of Participants

*10.1* Local Number of Participants to be Consented: 75 people will be consented and undergo the initial assessment for a minimum target of 30 participants completing the study.

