Since we do not have pilot data with adolescents using either of these interventions, we were unable to conduct a power analysis to calculate an appropriate sample size. Budget and time constraints necessitate a relatively small sample size. While some studies in the literature have reported significant effects using similarly small samples, we cannot be certain that the study is powered appropriately to confirm or refute our hypotheses. Therefore, we have framed the project with a primary goal of establishing feasibility (our ability to recruit, adolescents' acceptance of randomization, adolescents' tolerability of the interventions) and of collecting data that will allow a power calculation to determine the sample size necessary for the federal grant to follow this work.

15.3 Statistical Analysis: A p-value of .05 will be used to determine significance for behavioral measures and a p-value of .005 will be used to determine significance for neuroimaging measures. Paired t-tests will be used to compare baseline versus post-tDCS and post-MBT intervention for both intervention groups for biological, clinical, and behavioral measures. Between-group t-tests will be conducted on the side-effects to examine group differences in prevalence of side effects. Feasibility will be determined by looking at descriptive statistics about enrollment and eligibility of people that express interest in the study and enroll as well as retention of enrolled participants. Correlation analysis will be conducted to assess how changes in clinical and behavioral relate to biological measures following intervention. Mixed repeated measures ANOVAs will test our hypothesis that the active tDCS group will show greater change than the sham tDCS group with condition (active or sham) as the between participant measures; within-participant measures will include behavioral.

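### Feasibility is the primary goal, but section 6.0 shreds the pre-consent screening records and no log secures the eligibility and willingness-to-enrol rates

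*Combined protocol and SAP*

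**What the plan says.** - **Goal.** Section 15.2 reports that no power analysis was possible and gives the project a "primary goal of establishing feasibility (our ability to recruit", followed by acceptance of randomisation and tolerability. The hypothesis of Aim 1 in section 1.2 is: "We expect that adolescents will be willing to enroll in a randomized trial involving MBT and tDCS".
- **Measures.** Section 3.1 lists side effects and the "number of participants enrolled, and dropout rate" as the primary feasibility and tolerability measures.
- **Analysis.** Section 15.3 states: "Feasibility will be determined by looking at descriptive statistics about enrollment and eligibility of people that express interest in the study and enroll". The same sentence adds retention of those enrolled.
- **Targets.** Section 10.1 states: "75 people will be consented and undergo the initial assessment for a minimum target of 30 participants completing the study". Section 5.1 gives an "approximate final n of 15 per group".
- **Records.** Section 6.0 keeps phone-screen information only where the person takes part in the consent visit. For the others it states: "Phone screen information from individuals who do not qualify based on the phone screen or who decide not to enroll will be shredded".

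No section mentions a screening log, a tally of screen failures or refusals, or the recording of reasons.

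**The concern.** Willingness to enrol is a proportion: people who agreed, divided by people who appeared eligible and were asked. Eligibility among interested people is also a proportion, with everyone screened as its denominator. The people who complete both denominators are the screen failures and the decliners, and theirs are the records that section 6.0 destroys. After shredding, the information cannot be rebuilt.

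What is at stake is the part of the primary goal that lies before consent. Section 15.2 intends the data to support a larger federal grant application, and planning recruitment for that trial needs the yield per person screened. Section 23.1 argues that recruitment is feasible from an undergraduate population of over 30,000. Only a pre-consent yield would test that argument.

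**Working it through.** **1. The plan's own figures.** Two groups of about 15 give 2 × 15 = 30, which agrees with the minimum of 30 completers. No formula is given for the 75. The ratio 30/75 = 0.40 implies that 60% are lost between consent and completion, since 30/(1 − 0.60) = 75. That 60% is back-calculated. The documents neither state it nor divide it between baseline ineligibility, refusal and dropout.

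**2. Which steps keep their denominator.**

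| Step | Where the record arises | Secured by the plan? |
|---|---|---|
| Phone-screen eligible / screened | Phone or online screen (8.3) | No: records of those who fail are shredded (6.0) |
| Consented / phone-screen eligible | Phone or online screen, consent visit | No: records of those who decline are shredded (6.0) |
| Eligible at baseline / consented | MINI, MADRS-S and C-SSRS at baseline (5.2, 8.1, 8.2) | Yes |
| Randomised / eligible at baseline | After the home MBT sessions (5.3) | Yes |
| Completed / randomised | Follow-up assessments | Yes |

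**3. What the count of 75 can and cannot show.** Uptake = consented/screened. The number screened is an assumption, because the documents give none. Intervals are exact (Clopper-Pearson) 95% intervals.

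| Assumed screened | 75/screened | 95% CI |
|---|---|---|
| 100 | 75.0% | 65.3% to 83.1% |
| 200 | 37.5% | 30.8% to 44.6% |
| 300 | 25.0% | 20.2% to 30.3% |
| 500 | 15.0% | 12.0% to 18.4% |

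The same 75 fits every row.

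**4. A bare total of people screened would not be enough.** Uptake is (phone-screen eligible/screened) × (consented/phone-screen eligible). Suppose 300 were screened. With 100 eligible, it is 33.3% × 75.0% = 25%. With 200 eligible, it is 66.7% × 37.5% = 25%. The first case describes narrow criteria with willing candidates, the second wide criteria with reluctant ones. Only a record of eligibility and of agreement separates them.

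**5. The post-consent rates are not fixed by the target.** Suppose 75 consent and 30 complete:

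| Assumed randomised | Randomised/75 | Dropout = 1 − 30/randomised | 95% CI for dropout |
|---|---|---|---|
| 30 | 40.0% | 0% | 0% to 11.6% |
| 40 | 53.3% | 25% | 12.7% to 41.2% |
| 50 | 66.7% | 40% | 26.4% to 54.8% |

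These rates are informative and come from retained records.

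**The case against.** The best defence has four parts.

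- **Shredding individual records does not forbid anonymous counts.** This is correct, and it rules out saying that the pre-consent figures will certainly be lost. Some electronic traces may also survive. The screening MADRS-S sits in REDCap under a dummy ID (8.3), screening may be done by REDCap survey (8.3), and a landing page collects contact details from interested people (11.1). But the plan requires no tally and does not say how long these entries are kept. The MADRS-S covers one criterion, and the landing page records neither eligibility nor a decision.
- **Section 15.3 can be read narrowly, as people who express interest and also enrol.** On that reading the direct conflict with section 6.0 goes away, but the willingness named in Aim 1 is then not measured before consent at all.
- **Feasibility does not rest on one count.** This stands. A reader might infer that it does, but section 3.1 also lists side effects and dropout, and section 15.3 adds eligibility and retention.
- **The number enrolled is not empty.** This also stands. A reader might infer that recruitment simply runs until 30 complete, so that the count is fixed. No such stopping rule is written: 30 is a minimum, section 5.4 anticipates two years of data collection, and section 15.2 cites budget and time limits. Whether the targets are reached therefore carries some information. It does not reveal uptake.

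**Conclusion.** The concern holds for the steps before consent. As written, the plan does not secure the share of screened people who are phone-screen eligible, the share of those who consent, or the reasons for the rest. Its size can only be illustrated: with 100 to 500 screened, the planned 75 corresponds to an uptake of 75% to 15%. That range rests entirely on the assumed totals.

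Two stronger readings are not supported. A reader might infer that no eligibility or acceptance data will be available. Definitive eligibility is settled after consent and randomisation comes later still, so those steps, with dropout and retention, remain computable. A reader might also take 30/75 = 40% as a pass mark, or as the only yield that can be calculated. The documents do not present it as a criterion. It mixes baseline ineligibility with dropout, and it would be met automatically whenever both targets were met exactly.

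The randomised comparison is not affected. This is a cheap improvement, worth making because the loss falls on the stated primary goal and cannot be reversed.

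**What to change.** 1. **Section 6.0:** before any record is shredded, enter each screened person in a log without identifiers, giving the date, phone-screen eligible (yes/no, with reason) and agreed to the consent visit (yes/no, with reason). State that the log also covers people screened by REDCap survey. The date matters because the revision history (version 12) shows that the entry criteria changed during the study.
2. **Sections 3.1 and 15.3:** beside the number enrolled and the dropout rate, report these proportions, each with a 95% confidence interval:
   - phone-screen eligible/screened
   - consented/phone-screen eligible
   - eligible at baseline/consented
   - randomised/eligible at baseline
   - completed/randomised
3. For people already screened, recover whatever counts remain and report the period that the log covers.

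The cost is a tally sheet, a few sentences in three sections and a few minutes of staff time per screen. Because the log holds no identifiers, the privacy purpose of the shredding rule is kept.
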